## **3. INTRODUCTION**

As per International Conference on Harmonisation (ICH) E9 (1), the purpose of this document is to provide a more technical and detailed elaboration of the principal features of the analysis described in the protocol, and to include detailed procedures for executing the statistical analysis of the primary and secondary variables and other data.

This Trial Statistical Analysis Plan (TSAP) assumes familiarity with the Clinical Trial Protocol (CTP), including Protocol Amendments. In particular, the TSAP is based on the planned analysis specification as written in CTP Section 7 "Statistical Methods and Determination of Sample Size". Therefore, TSAP readers may consult the CTP for more background information on the study, e.g., on study objectives, study design and population, treatments, definition of measurements and variables, planning of sample size, randomisation.

R Version 3.3.2 with "DoseFinding" package (2) will be used for analyses based on Multiple Comparison Procedures and Modelling (MCPMod) and SAS® Version 9.4 will be used for all other analyses.

### 4. CHANGES IN THE PLANNED ANALYSIS OF THE STUDY

In the third paragraph in the 1346.9 CTP Section 7.1 (on page 65), the second sentence states "Change from baseline in everyday functional capacity as measured by SCoRS global ratings after 12 weeks of treatment is the secondary endpoint". This is inconsistent with the specifications in Section 5.1.2 in the CTP. It is clarified in this TSAP that the secondary endpoint in 1346.9 study is "change from baseline in everyday functional capacity as measured by SCoRS total score after 12 weeks of treatment".

### 5. ENDPOINTS

The primary objectives of this trial are to establish proof-of-clinical-concept (POCC) with respect to a non-flat dose-response curve together with the definition of one or more suitable doses with respect to the efficacy and safety of orally administered once daily dosing of BI 425809 in patients with schizophrenia on stable antipsychotic treatment. Table 5: 1 below lists the different endpoints and the corresponding measurement time points.

Screening (Visit 1) Day -28 to -7	Baseline (Visit 2) Day 1	Week 3 (Visit 3) Day 22 ± 3 days	Week 6 (Visit 4) Day 43 ± 3 days	Week 9 (Visit 5) Day 64 ± 3 days	Week 12 (Visit 6) or EOT Day 85 # + 3 days	Follow-up 1 EOT + 7 days ± 3 days
MCCB	MCCB		MCCB		MCCB	
	SCoRS				SCoRS	

Table 5: 1	Endpoints and time points of measurement
------------	--

		C pre,ss,3	C pre,ss,4 , C 2,ss , C 3.5,ss			
eC-SSRS	eC-SSRS	eC-SSRS	eC-SSRS	eC-SSRS	eC-SSRS	eC-SSRS †
BCVA #				BCVA		BCVA
F-M 100 #				F-M 100		F-M 100
Pupil diameter#				Pupil diameter		Pupil diameter
Anterior and posterior biomicroscopy exam #				Anterior and posterior biomicroscopy exam		Anterior and posterior biomicroscopy exam
IOP #				IOP		IOP
SD-OCT#				SD-OCT		SD-OCT
Fundoscopy#				Fundoscopy		Fundoscopy

† eC-SSRS is also measured at the second follow-up visit (end of study visit): FU2 (EOT + 28 days  $\pm$  7 days)

# Endpoints collected only in subjects participated in the ophthalmology sub-study

#### 5.1 PRIMARY ENDPOINT

Change from baseline in MCCB overall composite score at Week 12 is the primary efficacy endpoint. The MCCB overall composite t-score is derived from the seven domain scores obtained from a total of ten tests (see CTP Table 5.1.1: 1) and is measured at screening (Visit

1), baseline (Visit 2), Week 6 (Visit 4), and Week 12 (Visit 6). See CTP Sections 5.1.1 and 5.2.1 for details. A larger overall composite t-score indicates better cognition.

#### 5.2 SECONDARY ENDPOINTS

#### 5.2.1 Key secondary endpoint

There is no key secondary endpoint in this trial.

#### 5.2.2 Secondary endpoints

Change from baseline in SCoRS total score assessed by interviewer at Week 12 is the secondary efficacy endpoint. SCoRS total score is derived as the sum of non-missing responses from 20 interview-based items rated by an interviewer on a 4-point scale with higher rating indicating greater degree of impairment in day-to-day functions due to cognitive deficits. A response of "N/A" to an item is treated as missing. If six or more of the 20 items are missing for a subject at a visit, then the corresponding SCoRS total score is missing for that subject at the visit. If five or less of the 20 items are missing for a subject at a visit, then the item(s) with missing value(s) will be imputed first with the average of the non-missing item values, and then the SCoRS total score for the subject at the visit will be derived as the sum of non-missing item values and the imputed item values. SCoRS total score is measured at baseline (Visit 2) and Week 12 (Visit 6) or End of Treatment (EOT visit). See CTP Sections 5.1.2 and 5.2.1 for details.

For safety, the percentage of subjects with serious adverse event (SAE) (including clinically relevant abnormalities of physical examination, vital signs, electrocardiogram (ECG) test and laboratory tests) are secondary endpoint.

## **Boehringer Ingelheim**

 TSAP for BI Trial No: 1346.9
 Page 11 of 34

 Proprietary confidential information © 2020 Boehringer Ingelheim International GmbH or one or more of its affiliated companies

#### Boehringer Ingelheim TSAP for BI Trial No: 1346.9

Proprietary confidential information © 2020 Boehringer Ingelheim International GmbH or one or more of its affiliated companies

Page 12 of 34

#### 5.4.1 Variables from Ophthalmologic Sub-study

The following variables are collected at baseline (Visit 2), Week 9 (Visit 5) and one week after EOT (Follow-up Visit 1) and analysed for the ophthalmologic sub-study:

- Number of correct letters from the Best Corrected Visual Acuity (BCVA) test in each eye
- Total error score (TES) and level of color vision deficiency classification (i.e. low, average and superior discrimination) from the Farnsworth-Munsel 100 (F-M 100) hue testing in each eye
- Pupil diameter measurement in each eye

- Categorical changes (normal / abnormal) from the anterior and posterior biomicroscopy exam in each eye
- Intra-ocular pressure (IOP) in each eye
- Central retinal thickness in each eye as measured by the High Definition Ocular Coherence Tomography (SD-OCT)
- Categorical changes (normal / abnormal) from the indirect fundoscopy of the retina in each eye.

Changes from baseline to Week 9 and from baseline to follow-up visit 1 are derived for each of the above ocular measurements.

Please refer to Table 5: 1 for the different endpoints and the corresponding measurement time points.

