6.2.3 Follow Up Period and Trial Completion

Follow up visits will be conducted as described in the Flow Chart at 1 week after end of treatment to capture early withdrawal effects and at 4 weeks after treatment based on the half-life of the trial medication.

If patient discontinues trial medication early, termination of trial medication page must be completed and Follow-up Visits should be completed at 1 and 4 weeks after eEOT Visit.

Follow-up visit 1 (1 week after end of treatment) can be conducted as a phone contact. AEs which have not recovered at Follow-up Visit 2 should be followed until they are resolved, or deemed reasonably followed up by the investigator on consultation with BI.

Page 65 of 116

Proprietary confidential information © 2019 Boehringer Ingelheim International GmbH or one or more of its affiliated companies

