10.8 OPHTHALMOLOGIC SUBSTUDY

10.8.1 Flowchart

MAIN	Trial Periods	Screening Period	Randomized Treatment Period				End of Trial		
	Visit	1	2	3	4	5	6 EOT	Follow -up ¹	Follow up ²
	Study-Day	7 to – 28	1	22	43	64	85	EOT+ 7	EOT+ 28
SUB	Sub-study Visit	Screening				On- treatment		Post 1 ²	
	Time window for visits	-28 to -7 days				± 10		± 3	
	Sub-study Informed Consent	X							
	Best Corrected Visual Acuity	Х				X ¹		Х	
	Color Vision Test (F-M 100)	X				X ¹		Х	
	Pupil Diameter Measurement	X				X ¹		Х	
	Anterior / Posterior Biomicroscopy	X				X ¹		Х	
	Intra-ocular Pressure	X				\mathbf{X}^1		Х	
	Ocular Coherence Tomography	X				X ¹		Х	
	Indirect Funduscopy	Х				\mathbf{X}^1		Х	

¹Visual procedures to be completed at estimated peak exposure time point (120-300 minutes after dosing). Dosing on these days should be scheduled accordingly at the discretion of the investigator.

²If clinically relevant changes (compared to baseline) are documented at visit Post1 the same procedures need to be repeated at visit $FU2\pm10$ days. Further follow-up in case of ongoing AEs at the discretion of the investigator.

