BCVA will be determined using Early Treatment Diabetic Retinal Scale (ETDRS) charts at a 4-meter testing distance under standard, certified lighting condition (Precision Vision CAT N02425). ETDRS Chart 1(CAT 2111) will be used for the right eye, Chart 2 (CAT 2112) for the left eye and Refraction Chart R (CAT 2110) for the refractive error. If the patient is unable to read at least the 20/100 line, the test will be repeated with the distance reduced to one meter. For those unable to read the ETDRS chart at any distance, the following steps will be count fingers, hands movements and light/no light perception. The same optotype will be used for each patient throughout the study. The refractive error using Refraction Chart R will be determined at the baseline visit and collected throughout the remainder of the study period when BCVA is performed. Both eyes will be evaluated separately and the results captured in the eCRF, as well as the occurrence of any deviations from ETDRS chart reading.

Farnsworth-Munsell 100 hue test (F-M 100)

Color vision testing using the Farnsworth-Munsell 100 (Munsell Color Services Lab, X-Rite, Inc.) hue test will be used to evaluate each patient's category of color vision or color vision deficiency in both eyes, separately. It consists of 93 colors mounted in plastic caps, housed in four separate cases (Serial No. 555103180814, 08/2014). Each case consists of two hinged panels which contain a quarter of the 85 numbered, removable color caps. Two caps are repeated and fixed as pilot colors at either end of one panel in each case, making a total of 93 caps. Each hue cap between the fixed anchors can be adjusted as the observer sees fit. The

Proprietary confidential information © 2019 Boenringer ingemeint international Ginori of one of nore of its artifiated companies

final arrangement of the hue caps represents the aptitude of the visual system in discerning differences in color hue.

The standard software included in the FM 100 package will be used for scoring and analyzing the results. Total error score (TES) will be used as a measurement of color vision. Total error score and level of color vision deficiency classification (e.g. superior, average, low discrimination) will be recorded on the eCRF. Examination of color vision will be performed at during screening), Day 64 ± 10 (peak exposure), and at End of Trial + 7.

Pupil Diameter Measurement

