Dilated indirect fundoscopy of the retina will be performed in previously dilated eyes (topical mydriatic eyedrops) with a proper lens and either a slit lamp microscope or a light attached to a headband. Indirect fundoscopy of the retina will be performed at Day -1 (Baseline), at Visit 5 (Day 64) and at End of Trial. Results of normal or abnormal exams will be recorded on the eCRF, with further explanation and severity gradings (Grade 1-4) for abnormal results.

Photographs will be taken if a clinically significant abnormality is noted per ophthalmologist discretion.

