#### 6.7 BASELINE, TIME WINDOWS AND CALCULATED VISITS

In general, baseline values are the measurements taken on the day of the first administration of trial medication (Visit 2), and immediately prior to the first administration of trial medication. If this value is not available, the measurement at the screening visit (Visit 1) is used (PANSS and eC-SSRS), but this does not apply for MCCB measurement.

Visits are labelled according to the flow chart in the protocol: Visit 1 (screening), Visit 2 (randomisation and start of treatment, also baseline), Visit 3 (Week 3), Visit 4 (Week 6), Visit 5 (Week 9), Visit 6 (Week 12), and End of Treatment (EOT), Follow-up 1 (FU1) (7 days after EOT), Follow-up 2 (FU2) (28 days after EOT). Planned and actual test days are included in the analysis data sets and are calculated relative to the beginning of study as indicated in Table 6.7: 1 below.

Page 22 of 34

Visit	Relative to study start					
	Planned test day	Actual test day				
2	1	Day 1 – Day 2				
3	22	Day 3 – Day 39				
4	43	Day 40 – Day 60				
5	64	Day 61 – Day 81				
6 / EOT	85 for completed subjects	Day 81 – Day 101				
EOT	N/A (for early discontinued subjects)	Date of the last administration of trial medication to date of the last administration of trial medication + 8 days (for early discontinued subjects)				
FU1	EOT + 7 days	EOT + 4 days to $EOT + 10$ days				
FU2	EOT + 28 days	EOT + 21 days to EOT + 35 days				

Table 6.7: 1	Planned	and	actual	study	days
--------------	---------	-----	--------	-------	------

For efficacy endpoints with planned measurements at baseline, Week 6 and Week 12, actual measurement collected between Day 3 and Day 60 will be mapped to Week 6 and actual measurement collected between Day 61 and the actual EOT visit date will be mapped to Week 12, and baseline is the measurement collected at Visit 2. If multiple measurements are mapped into the same time point using the time window, then the first measurement will be used in the analysis.

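### The exploratory ophthalmologic sub-study aims at a comparison with placebo, but the only test the SAP adds is Week 9 versus baseline, with no placebo contrast; several sub-study texts also need reconciling (minor)

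*SAP*

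**What the plan says.** **Objective and testing.** Protocol 10.8.2 asks about the ocular safety of the four doses compared with placebo. Protocol 10.8.6 makes every ocular analysis exploratory, without formal endpoints. Protocol 10.8.7.1 excludes statistical testing and plans descriptive changes from baseline. SAP 7.8.5 plans summaries and shift tables, then adds a paired t-test and 95% CI of Week 9 against baseline for the continuous variables.

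**Baseline.** SAP 5.4.1 states: "The following variables are collected at baseline (Visit 2), Week 9 (Visit 5) and one week after EOT (Follow-up Visit 1"). The sub-study flow chart (protocol 10.8.1) and SAP Table 5:1 place the only scheduled pre-dose eye examination at Screening. SAP 6.7 takes baseline from Visit 2; if that is missing, "the measurement at the screening visit (Visit 1) is used (PANSS and eC-SSRS"), with no mention of ocular variables. For fundoscopy, protocol 10.8.5 has another version: "Indirect fundoscopy of the retina will be performed at Day -1 (Baseline").

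**Last visit.** Protocol 10.8.7.1 analyses Week 9 and Week 12 (Visit 6). The flow chart and SAP Table 5:1 schedule no eye examination at Visit 6, but one at Follow-up 1 (EOT + 7 days), which is what SAP 5.4.1 analyses. Footnote 2 of the flow chart also relies on that visit: repeat examinations follow if "clinically relevant changes (compared to baseline) are documented at visit Post1".

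**Week 9 window.** The sub-study flow chart allows ± 10 days, and the colour-vision text agrees: "Examination of color vision will be performed at during screening), Day 64 ± 10 (peak exposure"). The column heading of SAP Table 5:1 reads "Week 9 (Visit 5) Day 64 ± 3 days".

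**Enrolment.** Sub-study inclusion criterion 1 (protocol 10.8.3.1) asks that the patient can be expected to be randomized to active treatment. The trial is double-blind (protocol 3.1), and protocol 10.8.4 plans 16 to 20 evaluable placebo patients.

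SAP section 4, which lists changes to the planned analysis, mentions only the SCoRS endpoint wording.

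**The concern.** The drug has a stated potential for transient visual disturbances (protocol 1.2 and 2.3), and this is the dedicated ocular safety dataset. It has a randomized placebo group, yet the one inferential analysis does not use it. A change from baseline within an arm mixes any drug effect with whatever moves all arms alike, such as learning on the colour-vision test, retest effects or time. A significant paired result in a dose arm would therefore not show a drug effect, and a non-significant one would not show its absence. No estimate of the drug-placebo difference is planned.

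The remaining mismatches are of lesser weight. They leave the programmer and the reader unsure which examination is baseline, which late visit is reported and whether a test was meant to be run. The departures from the protocol are not declared where the SAP declares changes.

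**Working it through.** **1. The plan's own size.** Protocol 10.8.7.2 gives 10 per dose group and 20 on placebo: 4 × 10 + 20 = 60, which reproduces the stated minimum. The lower evaluable bound in 10.8.4 is 4 × 8 + 16 = 48. The size is not power-based, so there is no power figure to reproduce.

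**2. Assumptions.** The SAP does not say whether the paired test is run by arm or pooled. I read it by arm, because protocol 7.3.4 summarizes safety data by treatment received. Changes are taken as normal, arms as independent, the level as two-sided 5%, and one measure at a time. A shift δ common to all arms is in units of the SD of change, with no drug effect. No ocular SD is given, so δ = 0, 0.3, 0.5 and 0.8 are assumed values.

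**3. Formulas.**
- Paired test in an arm of size n: p(n) = P(|T| > t(0.975, n−1)), with T noncentral t on n−1 df and noncentrality δ√n.
- At least one of four dose arms flagged: A = 1 − (1 − p(10))^4.
- A dose arm flagged while placebo is not: A × (1 − p(20)).
- Dose-minus-placebo interval excluding zero for at least one of four doses: simulated with 100,000 runs, because the four contrasts share the placebo arm.

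**4. Results.**

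| Common shift (SD of change) | 0 | 0.3 | 0.5 | 0.8 |
|---|---|---|---|---|
| p(10), one dose arm | 0.050 | 0.136 | 0.293 | 0.616 |
| A, at least one of four dose arms | 0.185 | 0.443 | 0.750 | 0.978 |
| p(20), placebo arm | 0.050 | 0.247 | 0.564 | 0.924 |
| Dose arm flagged, placebo not | 0.18 | 0.33 | 0.33 | 0.07 |
| Placebo contrast, at least one dose | 0.17 | 0.17 | 0.17 | 0.17 |

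The fourth row is, for example, 0.443 × (1 − 0.247) = 0.334 at 0.3 SD and 0.978 × (1 − 0.924) = 0.074 at 0.8 SD. The last row does not depend on the shift, because a common shift cancels in the difference. Per dose it is about 0.05.

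**5. Precision (95% CI half-width, in SD of change).**
- Within an arm of 10: t(0.975, 9)/√10 = 2.262/3.162 = 0.72.
- Dose against placebo, 10 vs 20: t(0.975, 28) × √(1/10 + 1/20) = 2.048 × 0.387 = 0.79.
- At the lower evaluable numbers: 0.84 within an arm of 8, and 0.90 for 8 vs 16.

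**6. Number of intervals.** Acuity, pupil diameter, intra-ocular pressure and retinal thickness per eye, plus the averaged F-M 100 score: 4 × 2 + 1 = 9 measures. Over four doses this is 36 intervals, and 36 × 0.05 = 1.8 are expected to exclude zero by chance.

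**7. Windows.** Day 64 ± 10 is Days 54–74; Day 64 ± 3 is Days 61–67.

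**The case against.** The strongest reply is that little depends on this test. The analyses are exploratory, no decision rule uses the p-value, and ocular safety is also covered by ophthalmologist assessment, adverse event reporting and repeat examinations. That stands, and it is why the point is minor.

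Second, with no common shift the two approaches behave alike (0.19 against 0.17), and placebo results shown alongside would let a careful reader spot a shift. This stands in part. At 0.8 SD the placebo arm is nearly always flagged too, and a dose arm alone is flagged with probability only 0.07. At 0.3 to 0.5 SD that probability is 0.33, about twice the 0.17 of the direct contrast.

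Third, adding intervals also goes beyond the protocol's descriptive plan. Removing the p-value alone would restore the protocol. The contrasts are justified by the stated objective and should be labelled descriptive.

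Some stronger readings are tempting but not supported:
- A reader might infer that eye handling is undefined because averaging appears only for F-M 100. SAP 5.4.1 specifies each eye for every variable, and 7.8.5 makes the one exception. Averaging everything could dilute a change in one eye.
- A reader might infer that Week 9 examinations on Days 54–60 would be assigned to Visit 4. The mapping rule below SAP Table 6.7:1 is for efficacy endpoints, no eye examination is scheduled at Visit 4, and the ± 3 is the main-visit column heading.
- A reader might infer a defect because EOT can extend to "date of the last administration of trial medication + 8 days (for early discontinued subjects") and "Follow-up Visits should be completed at 1 and 4 weeks after eEOT Visit", so some Follow-up 1 examinations fall after the residual effect period. Those visits are meant to capture withdrawal effects, so this is not an error.

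**Conclusion.** The point holds at minor severity. The added paired t-test departs from the protocol's exclusion of testing and does not address the comparison with placebo, whether it is run by arm or pooled. Under an assumed common shift of 0.3 to 0.8 SD it flags at least one dose arm with probability 0.44 to 0.98 when there is no drug effect; with no shift the figure is 0.19. These numbers illustrate a mechanism. They rest on the by-arm reading and on shifts that no document gives, and they do not predict what the trial will show.

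The baseline conflict is mainly a label. A reader might infer that no valid ocular baseline exists, but only one pre-dose eye examination is scheduled, so the data to be used are not in real doubt. Week 12 in protocol 10.8.7.1 conflicts with the protocol's own flow chart, and the SAP's use of Follow-up 1 is undeclared. Criterion 1 may loosely mean entering the treatment period, but as written it conflicts with the blind and with the planned placebo patients. That is a problem in the enrolment text, not in the analysis. The primary MCCB analysis and the total of 504 are untouched.

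**What to change.** **Main change, SAP 7.8.5.** Remove the paired t-test. For each dose, show the dose-minus-placebo difference in change from baseline to Week 9 with a 95% CI, labelled descriptive and unadjusted. Keep the per-eye analysis of SAP 5.4.1 with averaging for F-M 100 only, and keep the summaries and shift tables.

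**Consistency corrections at the same time.**
- In SAP 5.4.1 and 6.7, define ocular baseline as the last pre-dose eye examination, scheduled at Screening. In protocol 10.8.5, reconcile the fundoscopy times (Day -1 and End of Trial) and the last colour-vision time (End of Trial + 7) with the flow chart.
- Reconcile protocol 10.8.7.1 with the flow chart on Week 12. Record in SAP section 4 that Follow-up 1 is analysed and how the testing plan differs from the protocol.
- Note in SAP Table 5:1 that the sub-study's Week 9 window is ± 10 days.
- Reconcile sub-study inclusion criterion 1 with the blind and with the placebo numbers in protocol 10.8.4 and 10.8.7.2.

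**Cost.** Wording only, with no extra examinations or patients. The output has 36 intervals, of which about 1.8 would exclude zero by chance. Each is slightly wider than its within-arm counterpart (0.79 against 0.72 SD), and at 8 to 10 patients per dose only large differences can be seen.

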Both left and right pupil measurements will be taken separately using a pupil gauge under standardized lighting conditions. Measurements for each eye will be recorded in the eCRF.

Anterior and posterior biomicroscopy

The anterior and posterior chamber slit lamp examination will be done in conjunction with a biomicroscope (for example Haag Streit BC900). The examination of the anterior segment and posterior segments will include the eyelid, sclera, conjunctiva, cornea, iris, lens, and the anterior vitreous. The binocular slit-lamp examination (stereoscopic magnified view of the ocular structures) will be also performed for further documentation of the ocular findings. The anterior and posterior chamber slit lamp examination will be performed in both eyes. Examination results of normal or abnormal will be indicated, and if abnormal to provide the condition and severity grading from 1-4 scale. Photographs will be taken if a clinically significant abnormality is noted per ophthalmologist discretion. Results will be recorded in the eCRF.

Intra-Ocular Pressure Measurement (IOP)

Intra-ocular pressure of both eyes will be measured separately (using the Goldmann applanation tonometry (Haag Streit AT900) or a similar device).

Spectral domain optical coherence tomography (SD-OCT)

High definition optical coherence tomography (spectral domain OCT) will be performed to evaluate the retinal and sub-retinal structures of both eyes. The central retinal thickness, along with other anatomical findings such as presence or not of intra-retinal fluid, sub-retinal fluid, and choroid and retinal pigmented epithelial layer changes will be documented and recorded in the eCRF. OCT images of both eyes will be captured and reported as normal or abnormal, and the central retinal thickness measurements will be recorded.

Further explanations and description of abnormalities will be provided for all abnormal results.

A central service vendor will be used to harmonize the OCT procedure and to centrally assess the results.

Indirect fundoscopy

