#### 7.8.5 Others

#### Ophthalmologic variables

#### Boehringer Ingelheim TSAP for BI Trial No: 1346.9

Proprietary confidential information © 2020 Boehringer Ingelheim International GmbH or one or more of its affiliated companies

Each ophthalmologic variable is measured for both the right eye and the left eye. For the total error score from F-M 100 test, the average of the total error scores from the right and the left eye will be used in the analysis.

For continuous variables, summary statistics including mean, median, standard deviation, minimum, maximum will be presented for the change from baseline measurements. In addition, paired t-test and 95% CI will be derived comparing Week 9 with baseline measurements.

For categorical variables, shift tables will be presented for the categorical changes from baseline.

 TSAP for BI Trial No: 1346.9
 Page 32 of 34

 Proprietary confidential information © 2020 Boehringer Ingelheim International GmbH or one or more of its affiliated companies

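### The ocular-safety sub-study plans no summary of its OCT readings, OCT structural findings or 1–4 severity grades, and the SAP is inconsistent on per-eye versus averaged colour-vision scores

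*SAP*

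**What the plan says.** **What is collected (protocol 10.8.5).** For OCT, beyond thickness, the "presence or not of intra-retinal fluid, sub-retinal fluid, and choroid and retinal pigmented epithelial layer changes will be documented and recorded in the eCRF". There is also an overall reading: "OCT images of both eyes will be captured and reported as normal or abnormal". A central vendor assesses the OCT results. For biomicroscopy, "Examination results of normal or abnormal will be indicated, and if abnormal to provide the condition and severity grading from 1-4 scale". Fundoscopy results are likewise normal or abnormal, "with further explanation and severity gradings (Grade 1-4) for abnormal results". The grades run from very mild (1) to severe (4). The Farnsworth-Munsell 100 hue test (F-M 100) is done on each eye separately.

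**What is analysed.** Protocol 10.8.7.1 and SAP 5.4.1 carry nearly the same list. OCT contributes central retinal thickness and nothing else. The biomicroscopy variable is "Categorical changes (normal / abnormal) from the anterior and posterior biomicroscopy exam in each eye", and the fundoscopy variable has the same two levels. SAP 5.4.1 also keeps, for each eye, letters read, pupil diameter, intra-ocular pressure, the F-M 100 total error score and the colour-discrimination class (low, average, superior). SAP 7.8.5 gives shift tables for categorical variables and change-from-baseline summaries for continuous ones. For the total error score, however, "the average of the total error scores from the right and the left eye will be used in the analysis".

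**The concern.** Protocol 1.2 and 2.3 name transient visual disturbance as a potential risk, and ocular safety is the sub-study's only objective (protocol 10.8.2). With about 10 patients per dose arm and no power calculation, individual new or worsened findings are much of what the sub-study can show. Three kinds of information that bear on this do not reach a planned ophthalmologic table:

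- an OCT that becomes abnormal, or shows new fluid or choroid or pigment-epithelium change, without a change in central thickness;
- an eye with an abnormality before treatment that becomes more severe on treatment;
- the full size of a colour-vision change confined to one eye, for the total error score.

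The sub-study tables could therefore show no shift while the eCRF holds findings that changed.

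**Working it through.** **Sub-study size.** Protocol 10.8.7.2 plans 10 patients in each of four dose groups and 20 on placebo: 4 × 10 + 20 = 60, which reproduces the stated minimum. The evaluable range in protocol 10.8.4 (8–10 per dose, 16–20 on placebo) gives 4 × 8 + 16 = 48 up to 60. Ten patients in a dose arm means 20 eyes.

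**OCT, collected against analysed.**

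| Item recorded in protocol 10.8.5 | Planned summary in protocol 10.8.7.1, SAP 5.4.1 or 7.8.5 |
|---|---|
| Central retinal thickness, each eye | Yes |
| Normal/abnormal reading, both eyes | None named |
| Intra-retinal and sub-retinal fluid | None named |
| Choroid and pigment-epithelium changes | None named |

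Biomicroscopy and fundoscopy get a normal/abnormal shift table. OCT, which has the same kind of reading and is centrally assessed, does not, and neither document says why.

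**Severity grades.** Code normal as 0 and the grades as 1–4. A worsening is a move from level a to level b with b > a.

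- All possible worsening moves: 5 × 4 / 2 = 10.
- Moves starting from normal, visible as normal to abnormal: 4 (0→1, 0→2, 0→3, 0→4).
- Moves starting from a grade, shown as abnormal to abnormal: 4 × 3 / 2 = 6 (1→2, 1→3, 1→4, 2→3, 2→4, 3→4).

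So 6 of 10 moves look like no change. This counts possible moves; it is not an expected frequency. The split also hides degree for eyes that start normal: an eye at grade 1 at Week 9 and grade 3 at Follow-up 1 reads as normal to abnormal on both occasions.

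Eyes with a pre-treatment abnormality can enter. The ocular exclusion in protocol 10.8.3.2 removes active conditions that, in the investigator's judgement, may interfere with the assessments, the analyses or their interpretation. It does not require a normal examination. The documents give no rate for such eyes, so their number cannot be estimated.

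**Total error score.** The analysed change is (right-eye change + left-eye change) / 2. If one eye changes by D and the other by 0, the result is D/2. With an illustrative D of 40 points it is 20. With +40 in one eye and −40 in the other it is 0. SAP 5.4.1 lists the score for each eye, so it does not match SAP 7.8.5. The averaging is not in protocol 10.8.7.1.

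**The case against.** **Adverse events already capture deterioration.** Protocol 10.8.5 has deterioration reported to the investigator. Protocol 5.3.7 asks for worsening of pre-existing conditions to be recorded as an AE. Protocol 7.3.4 counts events that begin before treatment and deteriorate under it as treatment-emergent, and SAP 7.8.1 tabulates AEs by arm. The sub-study flowchart (protocol 10.8.1) also requires repeat examinations after clinically relevant changes. All of this stands. A reader might infer that retinal changes would go unreported, and the documents do not support that: besides the AE route, thickness and fundoscopy are analysed in each eye. But whether an examination finding becomes an AE is a clinical judgement under protocol 10.8.5, and AE intensity (protocol 5.3.6.1) is judged by tolerance and interference with activity, not by the ophthalmic 1–4 grade. AE tables therefore do not show how many examined eyes changed in each arm.

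**The SAP follows the protocol.** A reader might infer that the SAP cut back the protocol's analysis. Apart from averaging the total error score, it did not: the narrow list is already in protocol 10.8.7.1. The gap is between what is collected and what is summarised.

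**Colour vision is not reduced to an average.** Correct. The discrimination class is kept for each eye and, being categorical, gets a shift table. A one-eye loss large enough to change class would show. Only the total error score is averaged, and averaging two eyes is a defensible summary for an oral drug.

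**The sub-study is exploratory, and grades are noisy.** No formal endpoints are defined (protocol 10.8.6). Grades are given where applicable, and ophthalmologists may deviate from the examination descriptions, so a one-grade move may be rater variation. A full five-by-five shift has 25 cells for 20 eyes in a dose arm. This argues for a simple count rather than a large table, but not for leaving the grades out of a plan whose purpose is description.

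**Parts of the public SAP are not visible.** A listing or table elsewhere cannot be excluded. Sections 5.4.1 and 7.8.5, where the ophthalmologic variables and displays are set out, name none of these summaries.

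**Conclusion.** The point holds as a gap between collection and planned summary. In the visible plan, the OCT normal/abnormal reading, the OCT structural findings and the 1–4 grades have no planned summary. The normal/abnormal shifts cannot show 6 of the 10 possible worsening moves, and SAP 5.4.1 and 7.8.5 disagree on whether the total error score is analysed per eye or averaged. Averaging halves a one-eye change.

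The conclusion rests on the text of those sections and on simple counting. It assumes nothing about how common pre-treatment abnormalities are, and it puts no number on affected patients. It does not extend to a claim that ocular harm would be missed by the trial as a whole. It concerns a descriptive sub-study, leaves the primary analysis untouched, and raises no question of clinical management.

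**What to change.** In SAP 5.4.1 and 7.8.5:

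1. Add a per-eye shift table of the OCT normal/abnormal reading by arm, from baseline to Week 9 and to Follow-up 1 (the time points SAP 5.4.1 already uses), with counts of new intra-retinal fluid, sub-retinal fluid, and choroid or pigment-epithelium changes.
2. Keep the normal/abnormal shifts for biomicroscopy and fundoscopy, and add by arm the number of patients with a severity-grade increase in either eye, or a grade-level shift (normal, 1–4) if preferred.
3. Reconcile the two sections on the F-M 100 total error score by summarising the per-eye or worse-eye change next to the two-eye average.

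The cost is SAP wording and a few descriptive tables from data already in the eCRF. No new examination or patient is needed, and the sample size stays at 60. The drawback is sparse cells at about 10 patients per dose arm, so the added tables should be read as counts, without inference.
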